10.12 Financial Considerations48

10.13 Recording, Access to and Retention of SourceData48

10.14 Electronic Case Report Forms49

10.15 Publications49

10.16 Audit/Inspections49

11 BIBLIOGRAPHY50

TABLE 2: TERMS, ACRONYMS, ABBREVIATIONS

The following abbreviations and specialist terms are used in this protocol.

6MWD	6 Minute Walk Distance
6MWT	6 Minute Walk Test
ABG	Arterial Blood Gases
AE	Adverse Event
ANSM	Agence Nationale de Sécurité du Médicament et des produits de santé
ATS	American Thoracic Society
BG	Blood Gas
BMI	Body Mass Index
BP	Blood Pressure
CAIRS	Coil Associated Inflammatory Response Syndrome
CAO	Coil Associated Opacity
CAT	COPD Assessment Test
CI	Confidence Interval
CO ₂	Carbon Dioxide
CoHB	Carboxyhemoglobin
COPD	Chronic Obstructive Pulmonary Disease
CPP	Comité de Protection des Personnes
CT	Computed Tomography
CV	Curriculum Vitae
DLCO	Diffusion Capacity for the Lungs for Carbon Monoxide
DSMB	Data Safety Monitoring Board
eCRF	Electronic Case Report Form
EDC	Electronic Data Capture
EQ-5D	EuroQol-5 Dimensions quality of life questionnaire
ERC	Eligibility Review Committee
ERS	European Respiratory Society
eTMF	Electronic Trial Master File
EU	European Union
FDA	Food and Drug Administration
FEV ₁	Forced Expiratory Volume in 1 second

GCP	Good Clinical Practice
Hg(mm Hg)	Mercury (millimeters of Mercury)
HR	Heart Rate
HRCT	High Resolution Computed Tomography
HU	Hounsfield Unit
ICF	Informed Consent Form
IEC	Independent Ethics Committee
IFU	Instructions for Use
IRB	Institutional Review Board
ITT	Intent-to-Treat
LAA	Low Attenuation Area
LoVR _{exp}	Mean Expiratory Lobar Volume
LVEF	Left Ventricular Ejection Fraction
LVR	Lung Volume Reduction
LVRS	Lung Volume Reduction Surgery
MCID	Minimum Clinical Important Difference
MCMC	Markov chain Monte Carlo
MedDRA	Medical Dictionary for Regulatory Activities
mMRC	Modified Medical Research Council
OUS	Outside United States
PA	Posterior anterior
PaCO ₂	Partial Pressure of Carbon Dioxide in Arterial Blood
PaO ₂	Partial Pressure of Oxygen in Arterial Blood
PFT	Pulmonary Function Testing
PHT	Pulmonary Hypertension
PI	Principal Investigator
PP	Per Protocol
QCT	Quantitative Computed Tomography
QOL	Quality of Life
RV	Residual Volume
RVSP	Right Ventricular Systolic Pressure
SAE	Serious Adverse Event
SAP	Statistical Analysis Plan

SDV	Source Data Verification
SGRQ	Saint George's Respiratory Questionnaire
SoC	Standard of Care
SOC	System Organ Class
SOI	Study Operations Instructions
SOP	Standard Operating Procedure
SD	Standard Deviation
T	Temperature
TLC	Total Lung Capacity
Tx	Treatment
UADE	Unanticipated Adverse Device Effect
US	United States
USADE	Unanticipated Serious Adverse Device Effect
VC	Vital Capacity

PROTOCOL SYNOPSIS

Reference	BTG-004517-01-FR
Title:	A Randomized Controlled Study of PneumRx Endobronchial Coil System Versus Standard-of-Care Medical Management in the Treatment of Subjects with Severe Emphysema (ELEVATE)
Sponsor:	Boston Scientific Corporation [name]
Timelines and duration:	Study Duration: All Subjects randomized to Treatment will be followed for 36 months post initial treatment. Subjects randomized to Control will be eligible to crossover and receive treatment as soon as possible. Crossover subjects will then be followed for 36 months post initial treatment. Control subjects who choose not to crossover will exit the study immediately. Expected Enrollment Start: Early 2018 Estimated Study Completion: First half 2023
METHOD	
Design:	Prospective, multicenter, open label, randomized (2:1), controlled study comparing outcomes in subjects treated with the PneumRx Endobronchial Coil System (Coil) to a medically-managed control group. The medically-managed control group will be eligible to crossover after 6 months.
Population:	The population studied included severe emphysema patients indicated for Coil treatment per the approved, CE marked Instructions for Use (IFU), who met the following inclusion criteria and did not meet any of the exclusion criteria. Inclusion Criteria: 
 1. Read, understood and signed the Informed Consent form 2. Meets indications for use per the IFU 3. Bilateral heterogeneous and/or homogeneous emphysema 4. 15% predicted \leq Post bronchodilator Forced Expiratory Volume in 1 second (FEV₁) \leq 45% predicted 5. Post bronchodilator Residual Volume (RV) \geq 200% predicted 6. Post bronchodilator Total Lung Capacity (TLC) $>$100% pred. 7. Post bronchodilator RV/TLC $>$55% 8. Dyspnea related to hyperinflation scored \geq 2 on modified Medical Research Council (mMRC) dyspnea scale despite optimal medical management 9. Receiving optimal drug therapy and medical management according to clinical practice. 10. Performing regular physical activity, at least 2 times per week ¹

¹ The World Health Organization defines physical activity as any bodily movement produced by skeletal muscles that requires energy expenditure – including activities undertaken while working, playing, carrying out household chores,

- | | |
|--|---|
| | 
 11. Stopped smoking as confirmed by carboxyhemoglobin (CoHB) 12. $100m \leq 6$ minute walk distance (6MWD) $\leq 450m$ 13. Deemed eligible per Eligibility Review Committee (ERC) 14. If treated in France, Subject must be entitled to French social security. 
Exclusion Criteria:
 
 1. Known sensitivity to drugs required for performing bronchoscopy or in whom bronchoscopic procedures are contraindicated 2. Evidence of active infection in the lungs 3. Hypersensitivity or allergy to nitinol (nickel-titanium) or its constituent metals 4. Clinically significant pulmonary fibrosis 5. Clinically significant, generalized bronchiectasis 6. Clinically significant bleeding disorders 7. Patient taking immunosuppressive drugs other than steroids (e.g., for the treatment of cancer, rheumatoid arthritis, autoimmune disease, or prevention of tissue or organ rejection). 8. Primary diagnosis of asthma 9. Two (2) or more COPD exacerbations in the prior year, or 1 or more COPD exacerbations in the prior 3 months with indication for hospitalization assessment, according to GOLD 2017 recommendations². 10. Predominant small airways disease defined as significant bronchiectasis with sputum production (> 2 tablespoons daily) or significant bronchial wall thickening per High Resolution Computed Tomography (HRCT) 11. Percent Low Attenuation Area (%LAA) < 20% in the most damaged lobe of either lung. 12. Computed Tomography (CT) Imaging consistent with active pulmonary infection, significant interstitial disease or pleural disease 13. Severe bullous disease (defined by bulla > 1/3 of lung volume, or single bullous defect > 8cm) or significant paraseptal emphysema [defined by numerous large (>1cm) paraseptal defects in the target lobe comprising >5% of total lung volume]. Lung pathology of nodule not proven stable or benign 14. Radiographic confirmation of atelectasis or other scarring/fibrosis in areas of intended Coil implant 15. Use of more than 20 mg/day prednisone (or equivalent dosage of a similar steroid) daily 16. Severe pulmonary hypertension (Right Ventricular Systolic Pressure (RVSP) > 50 mm Hg (preferably measured by right heart catheterization) or other signs of Pulmonary Hypertension (PHT) with |
|--|---|

travelling, and engaging in recreational pursuits. For those with limited mobility, this should be done at least 2 days per week.

² Global Strategy for the Diagnosis, Management and Prevention of COPD, Global Initiative for Chronic Obstructive Lung Disease (GOLD) 2017

	
right ventricular dysfunction)
 
 17. Severe hypercapnia (PaCO₂ > 55 mmHg on room air) and/or severe hypoxemia (PaO₂ < 45mm Hg on room air, High altitude criterion: PaO₂ < 30 mm Hg) 18. Previous Lung Volume Reduction (LVR) surgery, lung transplantation, lobectomy, LVR devices or other device to treat COPD in either lung. 19. Diagnosed with alpha-1 antitrypsin deficiency 20. Diffusion Capacity of the Lungs for Carbon Monoxide (DLCO) < 20 % 21. Significant, recent or unstable cardiac disease defined as severe heart failure (Left Ventricular Ejection Fraction (LVEF) < 45% despite optimal medical management), unstable cardiac arrhythmia or coronary artery disease (angina on activity), or ischemic event in the past 6 months. 22. Body Mass Index (BMI) > 30 23. Participation in any other clinical study. 24. Subject is pregnant or lactating, or plan to become pregnant within the study timeframe. 25. If treated in France, Subject is a “personne vulnérable” as defined by French regulation

Eligibility Review Committee:
	
Final eligibility was confirmed by an expert panel of experienced interventionalists, the Eligibility Review Committee (ERC), prior to randomization.

Participating sites:
	
Up to 30 centers across Europe were invited to participate. Sites were selected based on their experience with the Coil System, expertise in interventional bronchoscopy and operational and multidisciplinary resource availability.


Visits and Assessments:
	
Baseline Visit:
 
After obtaining Subject consent, the Subject’s eligibility for Treatment was evaluated. Relevant medical history, medications, comorbidities, previous treatments of emphysema, physical activity / rehabilitation status, and baseline characteristics were collected and entered into the Electronic Data Capture (EDC) system. Pulmonary Function Test (PFT), pregnancy test, imaging (HRCT scan inspiratory and expiratory,), exercise testing (6 Minute Walk Test – 6MWT), dyspnea assessment (mMRC), quality of life (QoL) assessment (St Georges Respiratory Questionnaire (SGRQ), COPD Assessment Test (CAT), EuroQoL-5 Dimensions QoL questionnaire (EQ-5D), and blood gases (BG) were collected. Eligibility was reviewed by the ERC, and if deemed eligible, subject was randomized.
 
Procedure Visits:
 
Subjects will undergo the Coil treatment. One lung will be treated per procedure, with procedures separated by approximately 2 months. Lobar targeting will be based on quantitative CT (QCT) densitometry analysis and Coils will be placed in the lobe with the higher LAA as measured in Hounsfield units (HU) at a -950 HU threshold.

Procedure data, chest X-ray data, adverse event data, pregnancy test, and medications will be collected and entered into the EDC system.

Each center’s principal investigator (PI), or one primary implanter, will perform all coil treatments in ELEVATE. If necessary, a secondary implanter will also be trained as a back-up.

Follow-up Visits:

Follow-up visits should be conducted per the schedule below. Study specific follow-up visits should take place during exacerbation free periods defined as 30 days with symptoms within normal day-to-day variability.

12- and 36-month study follow-up visits will include:

- PFT
- AE review
- Medications
- Inspiratory and expiratory HRCT

Definition of visit windows:

Patients should have visits scheduled during exacerbation-free periods, defined as 30 days with symptoms within normal day to day variability.

Treatment/Control Group Subjects:

Visit:	Visit Window:
Baseline	Eligibility, Inclusion
Randomization	
Treatment 1	
Treatment 2	2 months +/- 4 weeks post 1st treatment
12 months post Treatment 1	12 months +/- 4 weeks post 1st treatment
36 months post Treatment 1	36 months +/- 4 weeks post 1st treatment

Device:
	
PneumRx Endobronchial Coil System (Coil)


Treatment:
	
The Coil System is a CE-marked implantable device that is indicated for use in patients with homogeneous and/or heterogeneous severe emphysema to improve quality of life, lung function, and exercise capacity.
 
The Coil System consists of sterile Endobronchial Coils which come in 3 different sizes (100 mm, 125 mm, and 150mm) and a sterile, disposable, single-procedure Delivery System consisting of a Cartridge, Catheter, Guidewire and Forceps.
 
The Coil System is designed for bilateral treatment using a therapeutic bronchoscope with a 2.8 mm working channel and fluoroscopy for visualization beyond the bronchoscope.
 
Post-treatment pulmonary rehabilitation or exercise program is strongly encouraged.

Primary Objectives:
	
The objective of the study is to prospectively confirm the safety and effectiveness profile of Coil treatment in consideration of the findings of previous Randomized Controlled Trials.
 
Co-Primary Effectiveness Endpoints:
 
 • Percent change in FEV₁ from baseline to 6 months and • Change in SGRQ from baseline to 6 months

Management of Adverse Events
	
Safety information will be collected on an ongoing basis throughout the study as participating centers become aware that an adverse event has occurred. Serious Adverse Events (SAE) and specific respiratory Adverse Events (AE) of interest will be recorded on the AE form in the EDC system by the investigator or authorized designee. Event, date of onset, severity, seriousness, duration, and relationship to the procedure/device will be recorded. All AEs will be followed until they are adequately resolved or stabilized or study completion/ termination, whichever comes first.
 
An AE or suspected adverse reaction is considered "serious" if, in the view of either the investigator or sponsor, it results in any of the following outcomes:

	
Death, Led to serious deterioration in the health of the subject that either resulted in A life threatening illness or injury, or A permanent impairment of a body structure or a body function, or In-patient or prolonged hospitalization, or Medical or surgical intervention to prevent life-threatening illness or injury or permanent impairment to a body structure or a body function Led to fetal distress, fetal death or a congenital anomaly/birth defect.
 
Information on Specific Respiratory Events of interest will be collected and analyzed via event specific case report forms. These events of interest include:
 
 • COPD exacerbation • Hemoptysis • Pneumothorax • Lower Respiratory Tract Infection/Pneumonia • Tissue Reaction, Localized (a.k.a. Coil Associated Inflammatory Response Syndrome (CAIRS), also called Coil Associated Opacity (CAO) in the IFU)

Statistical Analyses:
	
The co-primary effectiveness endpoint will be analyzed on the intent-to-treat (ITT) population through the 6-month visit, using descriptive statistics to summarize results separately for treatment and control groups. No comparative inferential statistics will be conducted.

	
Safety analyses will be conducted on the safety population defined as those subjects who enter the bronchoscopy suit for the initial Coil

--	--

	
procedure. AE and SAEs will be summarized by Treatment group based on MedDRA codes. Incidence rates through 6 months will be summarized for treatment and control groups. Events will also be summarized by relevant, discrete time periods including the Treatment recovery period (30 days from either treatment).
 
Descriptive statistics will summarize percent change in FEV₁ as well as AEs and SAEs at 12 and 36 months follow-up for all coil treated subjects.

RESULTS	

Number of subjects to be analyzed
	
A total of 120 Subjects were randomized in a 2:1 ratio of Treatment to Control, respectively (80 Treatment group subjects, 40 Control group subjects).

Duration of the follow-up	Subjects will continue in the study through 36 months from first Coil implant. If Control subjects don't participate to crossover, they will exit the study immediately.
----------------------------------	--

The trial will be conducted and documented in accordance with the Declaration of Helsinki, the protocol, ISO 14155:2011 E, Clinical investigation of medical devices for human subjects – Good Clinical Practice, applicable laws and regulatory requirements specified in the protocol, and the stipulations of the clinical trial agreement.

1 SCHEDULE OF VISITS

Treatment/Control Group Subjects:

Procedure / Assessment	Baseline	Randomization	Treatment (Tx) 1*	Treatment (Tx) 2 ⁺⁺⁺	12 Month post treatment Follow-Up Visit ⁺⁺⁺	36 Months post treatment Follow-Up Visit ⁺⁺⁺
Informed Consent	X					
Baseline Assessment ¹	X					
Randomization	X	X				
Procedure Treatment	X		X	X		
Medications	X		X	X	X	X
AEs			X	X	X	X
PFTs including Lung volumes and Spirometry	X				X	X
6MWT	X					
QOL (SGRQ, mMRC, CAT, EQ5D)	X					
HRCT (inspiratory and Expiratory)	X				X	X
Chest X-Ray	X		X ²	X ²		
Pregnancy test	X		X	X		

¹Includes demographics, medical history, physical exam, vitals, echocardiogram, and additional pre -treatment evaluations (e.g. blood panel, blood gas).

²At procedure visits, a Chest X-Ray or a still fluoroscopic image will be performed immediately post procedure. A second chest X-Ray should be done before discharge, a minimum of 4 hours following the first chest X-Ray.

*No more than 45 days post baseline visit

⁺⁺⁺ 2 months ±4 weeks post initial coil treatment

⁺⁺⁺ ±4 week

2 BACKGROUND

2.1 Disease Background

[figure not shown]
Emphysema is a chronic respiratory disease with an estimated global prevalence of 1.8% (Halbert, 2006). Emphysema is characterized by gradual destruction and disappearance of alveolar walls. This results in reduction in the elastic recoil pressure of the lungs, and allows the smaller airways to collapse prematurely during exhalation, resulting in hyperinflation, air trapping, and diaphragmatic flattening with decreased diaphragmatic efficiency. This hyperinflation worsens with rapid breathing associated with exercise. These effects are believed to be a primary contributor to the dyspnea experienced by emphysema patients (O'Donnell, 2006). The alveolar wall damage also creates large nonfunctional air pockets or bullae that become physiologic dead space in the thorax, preventing healthier portions of the lung from expanding and contracting normally. Patients with advanced emphysema also frequently demonstrate collateral ventilation both within the affected lobes and even across lobar fissures. As the disease progresses, emphysema patients develop progressive increases in Residual Volume (RV) and Total Lung Capacity (TLC) which lead to dyspnea. Eventually patients also develop hypoxemic due to progressive loss of alveolar capillary membrane surface area. Hypoxemia and deconditioning contribute to muscle weakness and fatigue. The crippling effects of end-stage emphysema include severe dyspnea, severe limitation of activities, recurrent lung infections, and ultimately respiratory failure, which can result in death.

There are several treatments available for emphysema including medications, physical therapy, supplemental oxygen, endobronchial valve procedure, and surgery. Smoking cessation is important in the treatment of emphysema to limit the rate of progression of the disease. Emphysema can also be treated with inhaled bronchodilators, inhaled corticosteroids, anticholinergics, theophylline, phosphodiesterase-4 inhibitors and supplemental oxygen. Emphysema patients are prone to exacerbations, usually due to respiratory infections, which are usually treated with antibiotics and/or systemic corticosteroids and frequently require emergency room visits and/or hospitalizations. Emphysema patients may undergo pulmonary rehabilitation exercises and training. There are also two surgical procedures available for treatment of severe emphysema: lung transplantation and lung volume reduction surgery (LVRS). Lung transplantation is a seldom used option because of the limited availability of donor lungs, low transplantation priority for emphysema patients relative to other rapidly fatal pulmonary diseases, and because of the advanced age of most emphysema patients. LVRS is major surgery that carries the risk of morbidity and mortality. Recently, less invasive bronchoscopic approaches have been developed and several approaches are being actively investigated in human clinical trials in Europe and the US.

2.2 General Description of Investigative Agent(s)/Device

The Coil System is designed to compress the areas of lung parenchyma most damaged by emphysema to allow more normal tissue to expand (**Figure 1**).

Figure 1 - Diagram of the Lung Volume Reduction Procedure Using Coils

The Coil has been designed to treat the specific patho-physiologic challenges of the emphysema disease state. Emphysema is characterized by loss of the lung's natural elastic recoil which causes unsupported airways to collapse during exhalation. This, in turn, causes air trapping and increased lung volume, which makes breathing difficult. The Coil is intended to compress lung parenchyma, create tissue tension, and restore radial support, thereby tethering open the airways to reduce airway collapse and air trapping. The Coils also compress diseased tissue to reduce hyperinflation and shift preferential filling from diseased tissue to healthy tissue. Exhalation is facilitated, as re-tensioned lung tissue helps to maintain airway patency.

Because the Coil acts by a simple mechanical action of tissue tensioning and compression, the desired effects are achieved without collateral ventilation interfering with treatment outcome. The Coil is deployed using a minimally invasive approach through a bronchoscope and requires no incision. The Coil is designed to treat emphysema patients regardless of their disease distribution; it is suitable for patients with homogeneous and/or heterogeneous (either upper lobe predominant disease or lower lobe predominant) emphysema.

The Coil System has been shown to improve QoL, exercise capacity, and pulmonary function in patients with emphysema (Sciurba et al., 2016; Slebos et al., 2015; Deslée et al., 2016; Shah et al., 2013).

2.3 Summary of Prior Clinical Experience with the Coil System

The Coil System received the CE mark on October 8, 2010 and has been commercially available in select European countries since that time. Over 7,000 Coil procedures have been completed in Europe and other markets where the Coil System is commercially available. Additionally, the Coil System has been studied in over 2,000 subjects across 8 clinical studies in the EU and North America, including a US pivotal randomized controlled study conducted to support future FDA approval.

3 TRIAL OBJECTIVE(S)

3.1 Trial Objectives

3.1.1 Primary Objectives

The primary objective of the ELEVATE study is to prospectively confirm the safety and effectiveness profile of Coils for the treatment of severe emphysema in consideration of the findings of previous randomized controlled trials.

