3.4 Primary Endpoint (s)

The Co-Primary Effectiveness Endpoint for the study is:

- Percent change in FEV₁ from baseline to 6 months
- Change in St. George's Respiratory Questionnaire (SGRQ) from baseline to 6 months.

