8 STATISTICAL CONSIDERATIONS

8.1 Trial Design and Determination of Sample Size

A total of 120 Subjects were randomized in a 2:1 ratio of Treatment to Control respectively (80 treatment group subjects, 40 Control group subjects).

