8.5 Efficacy Analyses

All effectiveness analyses will be analyzed on the ITT population through the 6-month visit, using descriptive statistics to summarize results separately for treatment and control groups. No comparative inferential statistics will be conducted. In addition, descriptive statistics will summarize percent change in FEV₁ from baseline to 12 and 36 months for all coil treated subjects. Baseline will be defined as the last measurement taken prior to coil treatment.

Descriptive statistics will summarize effectiveness endpoints at 12, 24 and 36 months follow-up.

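### The primary objective is to confirm effectiveness, but the planned analysis is descriptive only and the supplied protocol states no criterion by which a result would confirm it

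*Combined protocol and SAP*

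**What the plan says.** Section 3.1.1 sets this aim: "prospectively confirm the safety and effectiveness profile of Coils for the treatment of severe emphysema in consideration of the findings of previous randomized controlled trials". The synopsis, under Primary Objectives, says the same: "The objective of the study is to prospectively confirm the safety and effectiveness profile of Coil treatment".

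Section 3.4 opens with "The Co-Primary Effectiveness Endpoint for the study is" and lists two items: "Percent change in FEV₁ from baseline to 6 months" and "Change in St. George's Respiratory Questionnaire (SGRQ) from baseline to 6 months". The synopsis joins these with 'and'. Neither place says what result on either endpoint would count as success.

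Section 8.5 plans "descriptive statistics to summarize results separately for treatment and control groups" on the ITT population and adds: "No comparative inferential statistics will be conducted". The Statistical Analyses entry of the synopsis agrees.

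Section 8.1, whose heading includes determination of sample size, says only "A total of 120 Subjects were randomized in a 2:1 ratio of Treatment to Control respectively", with 80 and 40 per arm. Section 8.2 places the detailed methods in a separate SAP.

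**The concern.** The objective and the analysis do not match. The objective promises confirmation, and readers will give that word weight because it comes with randomization, a control arm and named co-primary endpoints. The analysis yields two sets of per-arm summaries and no stated way to turn them into a conclusion.

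If the report nevertheless says that effectiveness was confirmed, the rule behind that statement will have been picked with the results in view. The trial is open label and SGRQ is a patient questionnaire, so such a rule would have little protection against being fitted to the data. A split result, with one endpoint favourable and the other not, has no assigned meaning.

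**Working it through.** **What the supplied text contains**

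| Element needed to confirm | Where it might stand | What is there |
|---|---|---|
| Hypothesis, alpha | 8.5, synopsis | Excluded by design |
| Benchmark from earlier trials | 2.2, 2.3, 3.1.1 | Trials cited, no result quoted as a reference |
| Threshold per endpoint | 3.4, 8.5 | None. MCID is in the abbreviation list and papers on minimal important differences are in the bibliography, but no body section sets a value |
| Responder cut-off | 3.1.2 | Responder rates named, no cut-off |
| One or both endpoints | 3.4, synopsis | Not stated as a rule |
| Effect, SD or power | 8.1 | None |

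The only figure to check is the sample size: 80 + 40 = 120 and 80/40 = 2, so the split is consistent. With no effect size, SD, alpha or power given, 120 cannot be derived, and no implied target can be worked back from it.

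**How much an unstated rule could matter (illustration)**

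Assumptions, none of them from the documents except the arm sizes:
- all 80 and 40 subjects have 6-month data;
- there is no true effect on either endpoint;
- differences between arm means are approximately normal and signed so that positive favours coils;
- the correlation ρ between the two endpoints is 0 to 0.7;
- the decision rules are this review's own, and all are descriptive, so Section 8.5 would not forbid them.

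Standard error of a difference in SD units: √(1/80 + 1/40) = √0.0375 = 0.194.

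- Both endpoints numerically better: P = 1/4 + arcsin(ρ)/(2π). At ρ = 0 this is 0.250. At ρ = 0.7 it is 0.250 + 0.775/6.283 = 0.373.
- Either numerically better: 1 − P(both worse) = 1 − P(both better), by symmetry.
- Opposite directions: 1 − 2 × P(both better).
- Both better by at least 0.2 SD: the bivariate normal probability that both z-values exceed 0.2/0.194 = 1.03. At ρ = 0 this is 0.151² = 0.023.

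| Rule or event | ρ = 0 | 0.3 | 0.5 | 0.7 |
|---|---|---|---|---|
| Both better by ≥ 0.2 SD | 0.023 | 0.042 | 0.058 | 0.079 |
| Both numerically better | 0.250 | 0.298 | 0.333 | 0.373 |
| Either numerically better | 0.750 | 0.702 | 0.667 | 0.627 |
| Opposite directions | 0.50 | 0.40 | 0.33 | 0.25 |

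**The case against.** The best defence is that the descriptive analysis was chosen openly. The device is CE marked, the protocol states no superiority hypothesis, and confirming a profile can be read loosely as checking consistency with earlier evidence. That stands as far as it goes: the absence of a test is not an oversight, and this point does not ask for one. It does not remove the mismatch, because consistency with earlier trials also needs a reference value and none is given.

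A reader might infer more than the documents support in four ways.

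- *That no criterion exists anywhere.* Section 8.2 defers detail to a separate SAP that was not seen. A formal test there would contradict Section 8.5, but a descriptive threshold or benchmark would not. The claim is limited to the supplied protocol.
- *That the plan forces a yes-or-no verdict.* No section requires one. The concern is with any such verdict that is given.
- *That significance-based pass marks belong among the available rules.* Section 8.5 rules them out, so they are left out of the illustration.
- *That one-or-both is wholly open.* The label 'co-primary', the singular 'Endpoint' and the synopsis's 'and' lean towards reading the two together. That is a hint and not a decision rule.

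The illustration also assumes complete 6-month data. The documents give no completion figure, and the visit schedule in Section 1 shows no 6-month visit and SGRQ at baseline only.

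**Conclusion.** The concern holds for the protocol as supplied. The objective in Section 3.1.1 and the synopsis claims a property that the analysis in Section 8.5 does not have. Per-arm descriptive summaries without a benchmark, threshold or combining rule cannot support a conclusion that effectiveness was confirmed.

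The size can only be illustrated. Under the assumptions above, the chance of apparent confirmation with no true effect runs from about 2% to 8% (both endpoints better by at least 0.2 SD) up to 75% to 63% (either endpoint numerically better). The two endpoints point in opposite directions in 50% to 25% of such trials. These figures show the spread among possible rules. They do not predict which rule the sponsor would use. The argument here is about effectiveness; the same objective also covers safety, for which the supplied text likewise states no criterion.

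**What to change.** In Section 3.1.1 and the synopsis, replace 'prospectively confirm' with 'describe'.

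Add to Section 8.5: *No success criterion is set for the co-primary endpoints; results will not be reported as confirming or failing to confirm effectiveness, and FEV1 and SGRQ will be reported together whatever their direction.*

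Do not add a statement that neither endpoint alone supports an effectiveness conclusion. It would imply that the two together might, and so bring back part of a decision rule. Nor should a pass mark be set now: Section 8.1 reports randomization in the past tense, and the trial is open label.

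The change needs no new data, visits or patients and alters no planned table. It does need a protocol amendment, approved by sponsor and investigator and submitted to the ethics committee under Section 10.7. The sponsor also gives up the word 'confirm' for this trial.
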